5.3 End of Study Definition

A patient participant is considered to have completed the study if he or she has completed the baseline visit, and both three and six month telephone interviews. If he/she is selected to participate in the “debriefing”, completion of the study is considered after the above has been completed and the “debriefing” has been completed.

A clinic personnel participant is considered to have completed the study if he or she has completed the formative evaluation (Aim 1); and the standard and targeted decision aid implementation strategies (Aim 2).

If he/she is selected to participate in the semi-structured interview (Aim 3), completion of the study is considered after the interview is completed.

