Three and six month follow-up surveys will be conducted by telephone or email (for those who have email access) to reduce patient participant burden. If requested, surveys will be mailed from the Data Coordinating Center (DCC) to patient participants, and will include a pre-stamped return envelope. Reminders will be sent to non-responders 1- and 2-weeks after the initial survey has been completed. Those who have an email will have the option to receive follow-up email reminders. If the reminders are not successful, surveys will be sent to non-responders via U.S. mail.

Patient participants will receive check-in phone calls and appointment reminders from the study coordinator prior to the three and six month follow-up surveys. In the event that a participant is a no-show for their clinic appointment, she/he will be recruited at their next clinic appointment.

The tailored, patient-targeted activities such as pre-visit web-based portal messages with access to the decision aid and information on the study time demand; will retain patients by maintaining a stream of consistent information. Each site will choose a tailored patient-targeted activity to display information about the study via patient portal, clinic poster, waiting room TV/online kiosk, and paper-based versions of the decision aid.

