Sites will also have the option to choose from recommended Tailored Implementation Activities. These strategies are clinic-targeted and patient-targeted activities designed to stimulate participant recruitment and retention. Sites will choose either activity that is most relevant for implementation of the DA at their clinic and we anticipate that some sites will choose both activities. At the end of the study, all sites will be reviewed to determine with strategies were used throughout the duration of the study.

Clinic-targeted Activities:

- DA reminder in patient intake process
- Audit and feedback
- Team huddles/clinic meetings

Patient-targeted Activities

- Pre-visit web-based portal messages with
 - Access to decision aid via a link
 - Information regarding the study time demand
- Pre-visit delivery of paper-based version of decision aid
- Clinic poster about decision aid
- Decision-aid information through the waiting room TV/online kiosk

The DA will be given to all patient participants that meet the eligibility criteria during their regularly scheduled lupus clinic visit. Before reviewing the decision-aid, patients will view a short educational video on the purpose and use of the decision-aid. Questionnaires and the DA will be administered on an iPad, and questionnaires will take no more than 30 minutes on average, to keep responder burden low. Three and six-month follow-up questionnaires will be administered via phone, mail, or at the regularly scheduled clinic visit per the patient participant preference, and will last no more than 15 minutes.

In the event clinic personnel transition to a different position or leave the organization, they will be given a Clinic Personnel Exit interview* to assess the reason for departure, their view on the dissemination of the decision-aid into normal clinic flow, and the sustainability for future use.

Aim 2 Clinic Personnel Survey

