The baseline visit will take approximately 1 hour to complete. All patients with lupus are eligible. The study coordinator will approach patients at their regularly scheduled lupus clinic appointments. Once the potential participant checks in either at a kiosk or with a front desk clerk, they will be made aware of the lupus decision-aid by either the clinic clerk or the study coordinator. The study coordinator will then approach the patient participant and invite them to participate in the study. If a patient participant declines the invitation to participate, the reason will be recorded in the excel spreadsheet. If the patient participant agrees to participate, he/she will be given a non-signature consent form which

explains the study objectives. The patient participant will be given the necessary time to read the non-signature consent form and ask any questions they have to the study coordinator. No signature will be necessary on the consent form. Participants will be required to sign a paper HIPPA form since study coordinators will view limited personal health identifiers (PHI) (medical record number, voice from conversations with physicians). The coordinator and patient participant will be required to sign the HIPPA form, and a copy will be given to the patient participant, as well as being placed in their file.

After the non-signature consent form is given to the patient participant, study procedures will begin and a participant number will be assigned. During the baseline visit, the following procedures will be performed and information will be obtained to determine eligibility to continue in this research study:

- Review inclusion/exclusion criteria
- Date of birth
- Self-reported race/ethnicity

Patient participants will be invited to watch a short informational video on the iPad and review the DA, before beginning the assessments. After completing the questionnaire, patients will complete a W-9 form that allows payment to be processed. Participants will be compensated via a paper check from the Data coordinating center that will take up to 7 business days to be issued, per institutional accounts payable procedures. Patient participants will receive payment (\$50) after the initial visit has been completed.

Each patient participant will be reminded of the three and six month follow-up phone calls prior to the visit departure.

Specific Aim 2: Follow-up Patient Participants

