 - a. make sure that the patient understands the study, is providing an informed consent to participate in the study and that he/she has had the opportunity to ask any questions.
 - b. guide the patients to the link where the lupus decision-aid aid (educational tool) can be viewed by the patient remotely on their phone, touchpad or a computer, per patient preference.
 - c. Confirm that patient is able to click on the link and see the decision-aid (see details on next page under the title: **Subject: Dr _____ - Lupus Survey (Page 3)**)
 - d. When the DA viewing ends, the survey completion link is on the last page. Remind the patient of this.
 - e. Schedule a follow-up call for later that day or the next day to follow-up for trouble-shooting or hear about their experience (de-brief): whatever we learn with the first few patients will make the process better quickly
5. Study coordinators complete the follow-up call within 24-hours and let [contact] know so she can check the data capture. This also helps the site process patient remuneration without delay.
6. Study coordinator will inform patient's lupus care provider prior to their virtual visit (the day of the visit or 1-day before the visit) with email and paper note on the schedule (or both), that the patient has viewed the lupus decision aid at home, so that any questions related to the information can be addressed during their virtual visit. For sites that allow the recording of the telehealth visits, it will be recorded for IDEAL. We will have to figure out how site can securely send the recording to us.

3- and 6-month VISIT = Virtual Visit via phone with study coordinator or self-directed web-based survey (Exception: if patient is in clinic within 4 weeks prior to 3- or 6-month visit, complete it during clinic visits)

1. Phone call: Call and complete the survey as previously on the phone. **PRO:** you are done in 20-25 minutes once you reach a patient, and there are only 2 follow-ups in a 6-month period.
2. Study coordinator calls the patient and asks them if they prefer to complete the survey themselves:
 - a. Send the anonymized link (Provided by UAB) in real time to the patient via phone/text reminder/web link during the phone call with the use of speaker phone by the patient
 - i. make sure they have a link on their phone or email that works

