 - ii. Help the patient put in the patient ID and site location ID as follows, so no room for error exists- these are forced responses, so survey will not get "submit" without these and we won't know who filled it, if missed:
 1. Click "_____ month survey"
 - a. Site Location ID: **UCLA-04**
 - b. Patient ID: **04_____**
 - c. Answer the remaining questions
 - iii. Urge the patient to continue and complete the survey when the phone call ends, so that they don't lose the link and get frustrated
 3. Study coordinator to follow-up with the patient via text or email: ask them if they completed and if they had feedback about the process

4. Study coordinator emails [contact] with patient ID and day of completion within 24 hours to check the completion of each patient survey. Please also send aggregate weekly log as previously noting in-person versus self-directed web-based survey completion

Subject: Dr _____ - Lupus Survey

Hello _____,

My name is _____, and I work with Dr. _____ at UCLA Rheumatology. I hope that you have been staying healthy and well.

I am e-mailing you in regard to a research study that you are currently participating in, IDEAL (Implementing the Decision-Aid for Lupus). At one of your recent rheumatology appointments, you reviewed a decision-aid for lupus and completed a survey.

This study is following patients three and six-months after their initial review of the lupus guide. We are interested in your views and opinions of this guide as well as your experience at our clinic, and would greatly appreciate your timely response to this survey. You will be **compensated \$10** for completion of this survey.

Instructions for Completing the Survey:

1. Please go to the following link (<http://www.thelupusguide.com/>)
2. Click "Next" under "Coordinator Begin Here"
3. If you are currently experiencing a lupus flare, choose "Real Flare"
 - a. If you are not experiencing a lupus flare, choose "Hypothetical Flare"
4. Depending on your language preference, choose either "English" or "Spanish"
5. On the following page, click "Click here" to view the decision aid

Steps 6-7 are optional

6. Click "Guide _____"
7. After you have finished reviewing the decision aid, repeat steps #1-5.

8. Click "____ month survey"
 - a. Site Location ID: **UCLA-04**
 - b. Patient ID: **04_____**
 - c. Answer the remaining questions

9. Please let me know once you have completed the survey by responding to this e-mail

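### Patient surveys move from iPad entry at baseline to mixed modes at 3 and 6 months, and the test of change over time neither adjusts for nor checks survey mode

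*Combined protocol and SAP*

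**What the plan says.** Baseline. Section 6.1 states "Questionnaires and the DA will be administered on an iPad", during a regular lupus clinic visit. Section 8 describes the same visit. The in-person alternatives added in Section 10.5 in 2020 (a link on the patient's own phone, or paper) are also filled in by the patient.

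Follow-up. Section 6.1 says "Three and six-month follow-up questionnaires will be administered via phone, mail, or at the regularly scheduled clinic visit per the patient participant preference". Section 5.8 words it as "Three and six month follow-up surveys will be conducted by telephone or email", with mail on request or for non-response. Section 8 has staff act as if a call is the norm: "Each patient participant will be reminded of the three and six month follow-up phone calls prior to the visit departure". Section 5.3 defines a completed patient as one who "has completed the baseline visit, and both three and six month telephone interviews". Section 10.5 offers a call with the study coordinator ("Call and complete the survey as previously on the phone") or a self-directed web survey, and it also permits text, email, mail and in-clinic completion.

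Recording. Section 10.5 asks sites: "Please also send aggregate weekly log as previously noting in-person versus self-directed web-based survey completion". The individual completion notice to the coordinating center carries patient ID and day of completion.

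Analysis. Section 9.1 sets no change over time as the null for clinic personnel and patient perceptions. Sections 9.1 and 9.4.2 test it with GEE that handles repeated measures and clinic clustering. Survey mode is not named in those models, in the subgroups (9.4.6) or in the sensitivity analyses (9.4.7). The bias sections (5.1, 6.2) deal only with selection of clinics.

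**The concern.** The patient outcomes are ratings of the decision aid (DA): usefulness, satisfaction, appropriateness and feasibility. People may rate differently when they speak to a coordinator than when they enter the answer themselves. Here the mode at baseline is largely fixed, and the mode at follow-up is a mixture that includes phone. Time point and mode therefore move together, and an estimated change from baseline contains both.

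Controlling for clinic does not help, because the shift occurs within clinic between time points. The text, email and web options added in 2020 also make the mixture depend on calendar period. If the phone share differs between sites, the comparison of trajectories by implementation strategy is exposed as well.

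At stake is how the main patient result is read. A rise could be reported as growing acceptance, or a fall as waning interest, when some of it reflects how the question was asked. Without mode on each record, nobody could check afterwards.

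**Working it through.** **Step 1. Mode by time point**

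| Time point | Permitted modes | Source |
|---|---|---|
| 0 months | iPad in clinic; from 2020 also own-phone link or paper | 6.1, 8, 10.5 |
| 3 and 6 months | Phone, mail, email, clinic visit; from 2020 also text and web link | 2.2 notes, 5.8, 6.1, 10.5 |

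Phone with a coordinator appears only in the second row. Clinic personnel surveys for Aim 2 are online at every time point (6.1, 8), so the point concerns patients only.

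**Step 2. The plan's own precision**

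Section 9.2 gives total 95% CI widths for a Likert mean of 0.09 (SD 0.5) and 0.35 (SD 2.0). Half-widths are 0.09/2 = 0.045 and 0.35/2 = 0.175.

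Reproducing them: width = 2 × 1.96 × SD / √n_eff, with n_eff = N / (1 + (m − 1) × ICC). For N = 16 × 35 = 560 and ICC 0.05, the design effect is 1 + 34 × 0.05 = 2.7 and n_eff = 560/2.7 = 207. The widths are then 0.136 and 0.544, so the stated ones are not reproduced. That is a separate matter. Both sets are used below only as yardsticks, and both describe a mean, not a change.

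**Step 3. Illustrative spurious change**

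Assumptions, not in the documents: phone answers differ by 0.1 to 0.3 points, and 50% to 90% of follow-ups are by phone.

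Spurious change = phone share × shift. Low: 0.5 × 0.1 = 0.05. High: 0.9 × 0.3 = 0.27.

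- Against 0.045 (stated, SD 0.5): the whole range is above.
- Against 0.175 (stated, SD 2.0): only the upper part is above. A 0.3 shift needs a phone share over 0.175/0.3 = 58%, a 0.2 shift needs over 0.175/0.2 = 87.5%, and a 0.1 shift never reaches it.
- Against the recomputed half-widths 0.136/2 = 0.068 and 0.544/2 = 0.272: the low end falls below the first, and the whole range falls below the second.

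**Step 4. Effect on a test of change**

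Further assumptions: SD 1.0, within-person correlation 0.5, the same design effect applied to change, two-sided 0.05, no true change. SD of change = 1.0 × √(2 × (1 − 0.5)) = 1.0. SE at 560 patients = 1.0/√207.4 = 0.069. Rejection probability = 1 − Φ(1.96 − b/SE) + Φ(−1.96 − b/SE), with b = share switching mode × shift.

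| Share switching | Shift 0.1 | Shift 0.2 | Shift 0.3 |
|---|---|---|---|
| 50% | 0.11 | 0.30 | 0.58 |
| 80% | 0.21 | 0.63 | 0.93 |

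The result depends on the SD. For 80% and 0.2 it is 0.21 at SD 2.0 and rounds to 1.00 at SD 0.5. More patients do not cure it: at 3,000 (design effect 1 + 186.5 × 0.05 = 10.3, n_eff 291, SE 0.059), 80% and 0.2 give 0.78.

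**The case against.** The strongest reply is that the plan offers patients a choice of mode to protect retention. That is reasonable in an implementation study that plans no imputation (9.4.7), and no document shows that mode shifts the answers. This stands as a reason not to restrict modes. It is not a reason to leave mode unrecorded.

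The exposure is also narrower than all of Aim 2. The 3- and 6-month surveys share one menu of modes, so the segment between them is less affected. A shift common to all implementation-strategy groups cancels when trajectories are compared. Both points stand, and the threat is mainly to overall change from baseline.

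A reader might infer more than the text supports:

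- *That baseline answers are private.* Baseline is in clinic with a coordinator involved. Under Section 10.5 the coordinator checks back with the patient or looks over the paper form. The contrast is self-entered against spoken answers, and self-entry on the iPad is itself inferred.
- *That follow-up is mostly by phone, with the person who recruited the patient.* Sections 5.3, 8 and 10.5 suggest phone was expected, but no share is given. Only the coordinator's role is named, not the individual.
- *That phone answers are more favourable.* No direction is given. A shift either way would distort a test of change.
- *That mail, web and clinic completers drop out.* Section 9.3 defines the Aim 2 population by questionnaires, whatever the mode. Its separate population of those who complete the trial is assigned to no analysis in 9.4. The telephone wording in 5.3 is an inconsistency with little consequence.

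**Conclusion.** The point holds for patient surveys. Mode changes with time point and calendar period, change over time is the tested hypothesis, and the plan has no mode term, no sensitivity analysis by mode and no stated mode variable on each survey record.

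The size is unknown. The 0.05 to 0.27 point range and the rejection probabilities rest wholly on assumed shifts, shares, SD and within-person correlation. It would be too strong to say that the artefact equals or exceeds the plan's precision. On the stated figures that is so throughout only at SD 0.5. This is a worthwhile, inexpensive improvement to how change from baseline is interpreted. It does not show that the result would be wrong.

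**What to change.** 1. Add a required field to every patient survey record for how it was completed: tablet in clinic, own device or web link, paper, or phone with a coordinator. For clinic completion, note whether the patient entered the answers. Recover past mode from site logs and the returned follow-up sheets where possible. Code the rest as unknown, so that the case-wise deletion in 9.4.7 does not drop those records from a model with a mode term.
2. In 9.4.2 or 9.4.7, pre-specify a sensitivity analysis of change from baseline limited to surveys self-completed at every time point. Report it beside the main estimate.
3. Add a mode term to the patient GEE as a supporting analysis only.
4. In 5.3, replace the reference to telephone interviews with follow-up surveys by any permitted mode.

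Cost: one survey field, some retrieval of past records, two extra analyses, and an amendment for IRB review. The downside is that mode is self-selected and nearly tied to time point, so adjustment is partial and the sensitivity set is smaller and may differ from the full sample.

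Changing the default follow-up mode or moving calls to Data Coordinating Center staff is not proposed. The first would add another break in mode partway through the study and might cost retention. The second needs staff.

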6.2 Measures to Minimize Bias

The observational study design explicitly incorporates varied context and baseline capabilities between the practices. This approach could lead to potential selection bias issues. To minimize the potential for selection bias, we have recruited clinics with varied characteristics both private and academic; general rheumatology and lupus clinics to implement the DA from a wide-range of geographical areas.

6.3 Implementation Strategy Fidelity and Adaptation

Study investigators will develop and work with clinic personnel to apply the standardized and tailored implementation activities within the clinic setting. It is expected that strategies will be adapted to suit each clinic's unique context and circumstances. We therefore expect to implement 16 different approaches. We will capture and describe each unique approach and use these findings to inform key outcomes. The periodic check-ins for each site following the Education, Training, and Refresher Training standardized activities will allow study personnel to determine the extent to which the DA has been implemented within clinic flow and processes.

Patient participant study compliance will be measured by completion of all study assessments, including the three and six month follow-up and semi-structured in-depth phone interviews. We will also assess whether or not the patient views the DA at the first visit at baseline and/or requests an electronic or paper copy of the DA (Aim 2).

7 STUDY INTERVENTION DISCONTINUATION AND PARTICIPANT DISCONTINUATION/WITHDRAWAL

7.1 Participant Discontinuation/Withdrawal from the Study

Participants (both patient and clinic personnel) are free to withdraw from participation in the study at any time upon request. Withdrawal will not affect the participant's future medical treatment or relationship with the physician. The participant may also revoke data authorization at any time by informing the study coordinator or investigator. There will be no penalty or loss of benefits owed if a participant decided to not participate.

An investigator may discontinue or withdraw a participant from the study for the following reasons:

- Significant study non-compliance
- If the participant meets an exclusion criterion (either newly developed or not previously recognized) that precludes further study participation

The reason for participant (either patient or clinic staff) discontinuation or withdrawal from the study will be recorded in the study database.

7.2 Lost to Follow-Up

A patient participant will be considered lost to follow-up if he or she fails to respond to multiple contact attempts. The following actions will be taken if a participant fails to return to the clinic for a required study visit:

- The study coordinator will attempt to contact the patient participant (mail, phone call, email).
- Before a participant is deemed lost to follow-up, the investigator or designee will make every effort to regain contact with the participant. These contact attempts should be documented in the participant's study file and the recruitment excel sheet.
- Should the participant continue to be unreachable, he or she will be considered to have withdrawn from the study with a primary reason of lost to follow-up.

8 STUDY ASSESSMENTS AND PROCEDURES

This study will be coordinated by the University of Alabama at Birmingham (UAB). All study visits and procedures will be performed at the United States, and at n = 16 sites. At least 35 participants are expected to be enrolled at each site. Enrollment will be competitive between sites.

Participants will be seen according to the details that follow:

Specific Aim 1: Clinic Personnel Survey/Semi Structured Interviews

This Specific Aim will: a) identify clinic staff and patient needs, and b) key contextual factors that inform targeted strategy selected influence implementation effectiveness, and sustainability. It will do so via two data collection efforts:

Clinic Personnel Survey

Up to 15 clinic personnel will be administered an online survey via Qualtrics® to assess their role in the clinic, clinic culture, and readiness to implement change. This will last between 20-25 minutes. Clinic personnel will be emailed a link to complete the survey. An automatic email will be generated in the Qualtrics® system and will go out to all non-responders every 24 hours for 5 days, or until the survey is completed.

Semi-Structured Interviews

Each site PI/ study coordinator will choose 6-8 key clinic staff that will be administered a 45-60 minute semi-structured interview either via phone or in person that will assess stakeholder needs and identify characteristics of the clinics (e.g., policy environment, physician, clinic, patient barriers) that influence DA adoption and choice of the implementation strategy. The interview protocol will be adapted to fit each time range and different key personnel. A link to the brief video animation introducing the decision-aid use and content along with the interview protocol and copy of the decision-aid will be emailed to clinic personnel prior to being interviewed. All interviews will be recorded and transcribed verbatim for accuracy.

Specific Aim 2: Implementation

Patient Baseline Visit

The baseline visit will take approximately 1 hour to complete. All patients with lupus are eligible. The study coordinator will approach patients at their regularly scheduled lupus clinic appointments. Once the potential participant checks in either at a kiosk or with a front desk clerk, they will be made aware of the lupus decision-aid by either the clinic clerk or the study coordinator. The study coordinator will then approach the patient participant and invite them to participate in the study. If a patient participant declines the invitation to participate, the reason will be recorded in the excel spreadsheet. If the patient participant agrees to participate, he/she will be given a non-signature consent form which

explains the study objectives. The patient participant will be given the necessary time to read the non-signature consent form and ask any questions they have to the study coordinator. No signature will be necessary on the consent form. Participants will be required to sign a paper HIPPA form since study coordinators will view limited personal health identifiers (PHI) (medical record number, voice from conversations with physicians). The coordinator and patient participant will be required to sign the HIPPA form, and a copy will be given to the patient participant, as well as being placed in their file.

After the non-signature consent form is given to the patient participant, study procedures will begin and a participant number will be assigned. During the baseline visit, the following procedures will be performed and information will be obtained to determine eligibility to continue in this research study:

- Review inclusion/exclusion criteria
- Date of birth
- Self-reported race/ethnicity

Patient participants will be invited to watch a short informational video on the iPad and review the DA, before beginning the assessments. After completing the questionnaire, patients will complete a W-9 form that allows payment to be processed. Participants will be compensated via a paper check from the Data coordinating center that will take up to 7 business days to be issued, per institutional accounts payable procedures. Patient participants will receive payment (\$50) after the initial visit has been completed.

Each patient participant will be reminded of the three and six month follow-up phone calls prior to the visit departure.

Specific Aim 2: Follow-up Patient Participants

We will follow each patient participant from screening for up to six months until completion of the full study (week 26). Unless the subject withdraws consent, the subject will be followed for the full study period and all data will be collected as scheduled. At three and six months post baseline visit, patient participants will be administered a 15 minute survey. Patient participants will receive a \$10 payment (via check) from Data Coordinating Center after each survey has been completed. Non-responders will be administered the survey on their next regularly scheduled lupus clinic visit.

Specific Aim 2: Clinic Personnel Survey

Up to 15 clinic personnel, the same clinic personnel as surveyed in Aim 1, will be administered an online survey via Qualtrics® at 0-, 6-, 12- and 24-months to assess their perception of appropriateness, acceptability, success, permanence and feasibility of the decision-aid. This will last between 20-25 minutes. Clinic personnel will be emailed a link to complete the survey. An automatic email will be generated in the Qualtrics® system and will go out to all non-responders every 24 hours for 5 days, or until the survey is completed.

Specific Aim 3: Semi-Structured Interviews

Clinic personnel interviewed for Specific Aim 1, as well as 2 participants at each site (selected by the site PI), will be administered a 45-60 minute, semi-structured phone interview. This interview will identify opportunities for sustaining and disseminating a lupus DA and help to develop a manual that provides a step-by-step implementation guide for incorporating lupus DA into regular clinical visits and care pathways for patients with lupus. This Specific Aim will result in: 1) knowledge of key lessons learned about the implementation process; 2) challenges to sustaining use of the DA; and 3) a manual that provides step-by-step implementation guide for incorporating lupus DA into regular clinical visits and care pathways for patients with lupus. Questionnaires will be adapted as in Specific Aim 1 to fit each time range, key personnel, and to account for any turnover in personnel interviewed in Specific Aim 1.

Study Coordinators

Every six months, a study coordinator from each site will be interviewed to evaluate the implementation of the DA and what can be done to improve the use and effectiveness within normal clinic flow. This interview will be administered via telephone. Non responders will be called every 24 hours for five days, or until a response is received.

